### **Adverse Event Information**

This study only collects leftover stool samples without any intervention done to the patients.

Therefore, there will be no additional risks to the patients apart from the standard care.

### **Limitations and Caveats**

1. Some participants cannot undergo colonoscopy for definite diagnosis of nosocomial diarrhea due to risk of procedures. These patients will be excluded from the study.

2. Number of participants in two groups were not equal as this is an observational study.

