## Data collection process

All patients are required to consent to the study. Their stool samples will be routinely sent for microscopic examination (cell count and parasites) and *C. difficile* toxin. Fecal calprotectin will be kept at -80 celsius degree and will be measured for fecal calprotectin at the end of study. The patients baseline characteristics, indication of hospitalization, treatment, and clinical progression will be obtained. All patients will be managed by primary physicians who do not know the results of fecal calprotectin level.

This protocol has been approved by Siriraj Institutional Review Board on January 24, 2019. The approval number is 718/2561(EC4).

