## Outcome Measures

Primary outcome: To determine the efficacy of fecal calprotectin in distinguishing inflammatory nosocomial diarrhea from non-inflammatory nosocomial diarrhea.

Secondary outcome: Correlation of fecal calprotectin levels and prognosis of hospitalized patients with nosocomial diarrhea.

The participants with nosocomial diarrhea were tested for C.difficile and stool examination or further colonoscopy for definite diagnosis group of diarrhea. Their leftover specimens will be kept until the end of the study. Then all collected stool specimens will be measured for calprotectin levels. Overall data collected of 147 participants will be completed analyzed about August 2020.

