### **Statistical Analyses**

The continuous data will be reported in mean and standard deviation or median and range as appropriate.

Categorical data will be reported in percentage or frequency.

Comparision of factors and patient characteristic between inflammatory and non-inflammatory diarrhea groups will be analyzed using independent t-test or Wilcoxon Rank Sum test for continuous variables, and chi-square test or fisher exact test for categorical variables.

Fecal calprotectin levels between inflammatory and non-inflammatory diarrhea will be shown in receiver operating characteristic curve(ROC). The best cut off will be calculated.

Correlation of fecal calprotectin levels and treatment outcomes, both univariate and multivariate analysis, will be analyzed by logistic regression.

P value < 0.05 will be considered statistically significant.

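### Patients left unclassified because they cannot have colonoscopy are dropped from the whole study, although the prognosis analysis does not need a diarrhea class

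*Combined protocol and SAP*

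**What the plan says.** Limitations and Caveats notes that "Some participants cannot undergo colonoscopy for definite diagnosis of nosocomial diarrhea due to risk of procedures" and continues: "These patients will be excluded from the study". The exclusion is not limited to any one analysis.

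The Outcome Measures section gives two aims. The primary aim is to separate inflammatory from non-inflammatory diarrhea. The other reads: "Secondary outcome: Correlation of fecal calprotectin levels and prognosis of hospitalized patients with nosocomial diarrhea". It names no diarrhea class.

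Under Statistical Analyses, the primary aim is served by a curve: "Fecal calprotectin levels between inflammatory and non-inflammatory diarrhea will be shown in receiver operating characteristic curve(ROC". A best cut-off and tests between the two classes go with it. For the secondary aim: "Correlation of fecal calprotectin levels and treatment outcomes, both univariate and multivariate analysis, will be analyzed by logistic regression". The covariates are not listed, and no separate analysis set is defined for this outcome.

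On data, Study procedures plans a calprotectin assay on every collected sample, and Data collection process states: "The patients baseline characteristics, indication of hospitalization, treatment, and clinical progression will be obtained".

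**The concern.** A missing reference diagnosis is a good reason to leave a patient out of an ROC curve. It is not in itself a reason to leave that patient out of a regression of outcome on calprotectin, where the diagnosis is neither exposure nor outcome. As written, the rule does both.

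Two things are at stake. The prognosis analysis loses patients and events, and its result describes only those who could be classified, although the stated outcome is wider. Separately, a reader of the ROC is not told how many patients fell outside it or what their calprotectin values were. The plan discloses the exclusion but does not plan to report this.

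**Working it through.** **1. Which analyses need the class**

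| Analysis | Needs a diarrhea class? |
|---|---|
| ROC curve and cut-off | Yes |
| Comparisons of characteristics between classes | Yes |
| Univariate logistic model, outcome on calprotectin | No |
| Multivariate logistic model | Only if class is a covariate (not stated) |

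**2. Who is affected.** The definitions classify some patients without colonoscopy. A positive toxin test or stool WBC above 5/HPF makes a patient inflammatory. A negative toxin test, no stool WBC and a response to diet together make a patient non-inflammatory. On the natural reading, the exclusion reaches only patients whom neither route classifies and who cannot have colonoscopy. Their number is not given.

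**3. When they leave.** The visible text points to exclusion after recruitment. Recruitment follows stool testing, the listed exclusion criteria do not mention colonoscopy, Outcome Measures places "further colonoscopy for definite diagnosis group of diarrhea" after the stool tests, and the caveat calls these patients participants. The enrollment flow chart (Figure 1) is not shown, so the timing is uncertain.

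**4. Size (illustrative).** The plan's 61 per group concerns the class comparison, and no power is claimed for the secondary outcome, so there is no plan figure to reproduce. From the documents come 147 ("Overall data collected of 147 participants will be completed analyzed about August 2020") and the 0.05 significance level, taken as two-sided to match the 1.96 in the sample-size section. The text does not say whether 147 is before or after the exclusion. Assumed: odds ratio 1.6 per SD of a standard-normal calprotectin score, 20% risk in retained patients, excluded share e of 10%, 20% or 30%, and excluded patients at equal or 2.5 times the risk.

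Numbers:
- If 147 is before exclusion, 147 × (1 − e) leaves 132, 118 or 103.
- If 147 is after exclusion, 147 / (1 − e) gives 163, 184 or 210, so 16, 37 or 63 could be added back.

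Hand approximation at equal risk: power ≈ Φ(ln OR × √(n·p·(1 − p)) − 1.96), with ln 1.6 = 0.470 and p(1 − p) = 0.16.
- n = 147: 0.470 × 4.850 − 1.96 = 0.319, power 62.5%.
- n = 132, 118, 103: 57.9%, 53.3%, 47.9%, so losses of 4.6, 9.2 and 14.6 points.
- n = 163, 184, 210: 67.0%, 72.2%, 77.8%, so gains forgone of 4.5, 9.7 and 15.3 points.

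Simulation of the unadjusted logistic model (Wald test, 20,000 runs per case, Monte Carlo SE about 0.35 points). Ranges span equal and 2.5 times the risk:

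| Excluded | 147 before: excluding v keeping | 147 after: excluding v keeping | Loss (points) |
|---|---|---|---|
| 10% | 54% v 59% | 59% v 63–64% | about 5 |
| 20% | 50% v 59–60% | 59% v 69–70% | 10–11 |
| 30% | 43–44% v 58–61% | 59% v 74–77% | 15–18 |

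Simulated powers are a few points below the hand values; the equal-risk differences agree closely.

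**5. Sensitivity**
- *Risk of the excluded patients, unadjusted model.* Equal versus 2.5 times the risk changes the loss by at most about 3 points. At 30% excluded and 2.5 times the risk, expected events (147 before) are 103 × 0.2 ≈ 21 when excluding, against 103 × 0.2 + 44 × 0.5 ≈ 43 when keeping. The extra events add little power because the pooled odds ratio falls from 1.6 to about 1.53–1.54.
- *With an 'unclassified' level in the model.* At 2.5 times the risk the odds ratio stays at 1.61–1.62, and the loss is about 7, 14 and 20–22 points at 10%, 20% and 30%. At equal risk it matches the unadjusted model.
- *Other odds ratios (unadjusted, 10,000 runs).* At 1.4 or 2.0 the loss is 3–4 points at 10% and 8–16 points at 30%.

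**The case against.** The strongest case against has four parts.

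- *The patients may never have been enrolled.* If the flow chart removes them at enrollment, no assay or outcome need exist for them. This stands as a limit: the point covers only patients recruited and sampled.
- *There may be few of them.* The stool and diet routes classify many patients, and nothing in the documents supports a share of 10% to 30%. This also stands. A reader might infer that everyone unfit for colonoscopy is dropped; the definitions do not support that.
- *The outcome is undefined.* Neither prognosis nor treatment outcomes is specified. If the outcome is response to treatment aimed at a diagnosis, unclassified patients may have no comparable value. This limits which outcomes can be used, but does not justify a blanket exclusion.
- *A single classified cohort is a defensible choice in a small observational study, and the exclusion is disclosed.* True, and this is why the point is an improvement rather than an error. Disclosure still does not supply the number or calprotectin values of those removed.

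A stronger reading is tempting. The exclusion is for procedural risk, which the Background links to comorbidity, so a reader might infer that the sickest patients leave and the prognostic odds ratio is biased. Losing sicker patients is plausible. However, exclusion related to risk does not by itself distort the calprotectin–outcome association, and the documents give nothing from which a bias could be shown.

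**Conclusion.** The point holds as a cheap improvement to consider. The plan applies to every analysis an exclusion that only the ROC, the cut-off and the class comparisons require. For patients recruited and sampled but left unclassified, this costs the secondary analysis precision and narrows its population.

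The true size is unknown, since the documents give no excluded share, event risk or odds ratio. On the assumptions above, the loss is small unless the excluded share is well above 10%. Confidence is medium because the timing of exclusion and the definition of the outcome are not settled by the visible text.

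The ROC itself is not faulted for omitting these patients: they have no reference diagnosis and cannot enter it. What is missing there is a description of them, without which the reach of the accuracy result cannot be judged.

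**What to change.** 1. Reword the caveat so that these patients are excluded from the ROC and other comparisons between diarrhea classes, not from the study.
2. Keep consented, sampled, unclassified patients who have an outcome in the prognosis regression, for any outcome that can be assessed without the diagnosis. If class is a covariate, give it an 'unclassified' level.
3. Beside the ROC, report the number, characteristics and calprotectin distribution of the unclassified patients.

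The cost is a wording change and one descriptive table, with no added colonoscopies. A few extra assays or outcome records are needed if exclusion would otherwise stop them. There are two downsides. Outcomes that depend on the diagnosis cannot be used for these patients. If their risk is higher, the pooled unadjusted odds ratio also moves slightly towards 1, which the 'unclassified' level avoids.

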### **Certain Agreements**

The principal investigator is not an employee of the sponsor.

